### 10.3 Safety Analyses

Four safety summaries will be reported from this registry.

Observational AEs: SAEs and AEs of Special Interest occurring from the first day in registry through the last contact (see definition in Section 10.3.1) irrespective of drug treatment duration.

Registry Treatment-Emergent AEs: SAEs and AEs of Special Interest occurring from the first dose in the registry through the last dose plus 70 days in the registry, excluding AEs occurring during TI period.

All Treatment Emergent AEs: SAEs and AEs of Special Interest occurring from the first recorded dose (initial dose) of MTX or Humira through the last dose plus 70 days in the registry, excluding AEs occurring during TI period. For patients enrolled from Study M10-444 and Study DE038, the total number of SAEs and AEs of Special Interest will include the events reported after the

first recorded dose of study drug in previous study, except those which occurred during the double-blind period in Study DE038 if the patient was in the Placebo arm during this period, any events reported by retrospective data collection, and events reported during this registry.

AEs for intermittent treatment: SAEs and AEs of Special Interest in the Intermittent Treatment Population through 10 years of the registry.

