## 5.0 Registry Objectives

The primary objective of this registry is to evaluate the long-term safety of Humira in patients with moderately to severely active polyarticular or polyarticular-course JIA who are prescribed and treated in accordance with the approved local Humira product label under the conditions of a routine clinical setting. Patients being prescribed and treated with MTX per the approved local product label will be considered a reference group.

The secondary objective of this registry is to evaluate the long-term effectiveness of Humira in patients with moderately to severely active polyarticular or polyarticular-course JIA who are prescribed and treated in accordance with the approved local Humira product label under the conditions of routine clinical setting. In addition, the impact of treatment interruptions on the safety and effectiveness of Humira will be evaluated as well. Patients being prescribed and treated with MTX per the local product label will be considered a reference group.

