### 6.1.1 Inclusion Criteria

The decision to prescribe either Humira or MTX must be made prior to the decision to enroll a patient in the registry. A patient will be eligible for participation if he/she meets the following criteria:

1. For a patient enrolling into the Humira arm; a pediatric patient diagnosed at any time with moderately to severely active polyarticular or polyarticular-course JIA (defined as arthritis affecting ≥ 5 joints at the time of diagnosis of polyarticular or polyarticular-course JIA) who has been prescribed Humira therapy according to the locally approved Humira product labeling and meets one of the following criteria:
  - a. Enrolled patients are 4 to 17 years of age as per approved Humira product label with the addition of polyarticular JIA patients 2 to < 4 years of age in countries with available local approval for this group of patients at the time of consent to the registry.
  - b. Newly initiated (within 24 months of registry entry) on Humira therapy and has received continuous (no more than 70 consecutive days off drug) Humira therapy, and the physician can provide available source documentation of SAEs, AEs of Special Interest, and dosing information since initiation of therapy;
  - c. Or is entering after participation (within 24 months of registry entry or, if longer, continuously treated at the same site) in an AbbVie Humira sponsored study, regardless of age or the number of joints with symptoms of polyarticular JIA, and has received continuous (no more than 70 consecutive days off drug) Humira therapy and the physician can provide available source documentation of SAEs, AEs of Special Interest, and dosing information since initiation of therapy.
2. For a patient enrolling into the MTX arm; a pediatric patient diagnosed at any time with moderately to severely active polyarticular or polyarticular-course JIA (defined as arthritis affecting ≥ 5 joints at the time of diagnosis of polyarticular or

polyarticular-course JIA) who is prescribed MTX therapy alone or in combination with other DMARDs according to the local product labeling (initiated treatment within 24 months of registry entry) and has received continuous therapy and the physician can provide available source documentation of SAEs, AEs of Special Interest, and dosing information since initiation of therapy.

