### **10.3.1 Analysis of Observational SAEs and AEs of Special Interest**

The number and percent of patients experiencing SAEs and AEs of Special Interest during the registry, regardless of whether the AEs are reported during or after the Humira or MTX treatment, will be tabulated by body system and Medical Dictionary for Drug Regulatory Activities (MedDRA®) preferred term. Rates (event per 100 patient year of observation) of SAEs and AEs of Special Interest and the 95% confidence interval will be provided. The AEs summaries will also include SAEs and AEs of Special Interest collected through the HCP process. The last contact date is defined as the last date of registry or direct to HCP process participation, whichever occurs later.

The summaries will be provided using data from the first day in registry through the last contact irrespective of drug treatment duration.

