### **10.3.2 Analysis of Registry Treatment-Emergent SAEs and AEs of Special Interest**

Registry Treatment-emergent SAEs and AEs of Special Interest will be summarized.

Registry Treatment-emergent AEs includes AEs occurring from the first dose day of the registry to 70 days after the last dose of registry drug excluding AEs occurring during TI period. The SAEs and AEs of Special Interest collected through the HCP process will not be included in this summary.

The number and percentage of patients experiencing registry treatment-emergent SAEs and AEs of Special Interest will be tabulated by body system and MedDRA® preferred

term. In addition, a summary of SAEs and AEs of Special Interest by severity and relationship to registry drug will be presented. Rates (event per 100 patient-years of registry exposure to Humira or MTX) of SAEs and AEs of Special Interest and the 95% confidence interval will be provided.

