### **10.3.3 Analysis of All Treatment-Emergent SAEs and AEs of Special Interest**

All Treatment-emergent SAEs and AEs of Special Interest includes events occurring after the first recorded (initial) dose of MTX or Humira (after the first recorded dose of study drug in previous study for subjects who rollover from Study DE038 or Study M10-444 into this registry), up to 70 days after the last dose of registry drug (excluding SAEs and AEs of Special Interest occurring during TI period and AEs which occurred during the double-blind period in Study DE038 if the patient was in the Placebo arm during this period). The SAEs and AEs of Special Interest collected through the HCP process will not be included in this summary.

The number and percentage of patients experiencing treatment-emergent SAEs and AEs of Special Interest will be tabulated by body system and MedDRA® preferred term. In addition, a summary of SAEs and AEs of Special Interest by severity and relationship to registry drug will be presented. Rates (event per 100 patient-years of total exposure to Humira or MTX) of SAEs and AEs of Special Interest and the 95% confidence interval will be provided.

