## **10.6 Determination of Sample Size**

The proposed sample size for this registry is approximately 800 patients. Due to the low incidence and prevalence of the disease, the size of the registry has been chosen based on the expected availability of eligible patients to be enrolled in a three year time frame. The estimated recruitment rates were based on published articles and advice from one leading pediatric rheumatology site.

It is planned that a total of 800 patients will be enrolled to this registry in a ratio of 5:3 corresponding to the Humira arm or the MTX arm respectively. The sample size determination is based on the rate of serious infectious AEs in the Humira arm. Assuming a total of 500 patients with full 5 years of follow up in the Humira arm, a maximum total exposure to the Humira in this registry can be 2500 patient years. Typically a higher rate of dropout is expected in a registry compared to traditional controlled studies. Allowing for approximately 68% dropout, a total of approximately 1500 patient years exposure in the Humira arm will have approximately 97% power, using a two-sided test at level of significance  $\alpha = 0.05$ , to detect a rate of serious infectious AE of 4.8 events per 100 patient years from the rate of 2.8 events per 100 patient years previously seen in this population in Study DE038.

Due to low frequencies of malignancies and congestive heart failure (CHF), patients will be followed for an additional 5 years.

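### No safety rate is planned by time since first dose or by registry period: three of the four summaries average over the whole window and the fourth splits only by treatment interruption

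*Supplement*

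**What the plan says.** Section 5.0 sets the aim: "The primary objective of this registry is to evaluate the long-term safety of Humira". Section 4.0 promises safety data for 10 years. Section 10.3 then says "Four safety summaries will be reported from this registry":

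- **Observational (10.3.1).** "SAEs and AEs of Special Interest occurring from the first day in registry through the last contact", with "Rates (event per 100 patient year of observation) of SAEs and AEs of Special Interest and the 95% confidence interval will be provided".
- **Registry treatment-emergent (10.3.2).** First registry dose to 70 days after the last, outside interruptions: "Rates (event per 100 patient-years of registry exposure to Humira or MTX", again with a 95% CI.
- **All treatment-emergent (10.3.3).** The same, but counted from the first recorded dose: "Rates (event per 100 patient-years of total exposure to Humira or MTX".
- **Treatment interruption (10.3.4).** Patients with and without an interruption, rates before and after the longest interruption, and a before/after shift table.

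Section 10.5 adds periodic safety assessments on cumulative data, with timing and content left to later decisions.

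Three other sections bear on this. Section 6.1.1 admits Humira patients "Newly initiated (within 24 months of registry entry) on Humira therapy", or later if they come from a sponsor study. Section 10.6 explains the second five years: "Due to low frequencies of malignancies and congestive heart failure (CHF), patients will be followed for an additional 5 years". Section 6.0 reduces collection from Year 6 to SAEs, pregnancies and a subset of AESI, except for children enrolled at 2 to under 4 years, who keep full collection.

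**The concern.** A person-time rate is a valid descriptive average, but it cannot show how risk moves with time on treatment, and that is what a long-term safety objective asks. A rise after several years is averaged with the larger body of earlier person-time. An excess soon after starting may fall largely before registry entry.

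The averages for the two arms also cover different stretches of treatment. Roll-over patients enter only the Humira arm, MTX exposure stops at the first Humira dose (Section 10.2), and a patient who switches starts a new 10-year clock in the Humira arm. Part of any difference between the Humira rate and the MTX reference rate could therefore reflect time on treatment.

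For AESI no longer collected after Year 5, a 10-year denominator mixes fully and partly observed time.

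**Working it through.** **Inputs.** From Section 10.6: 500 Humira patients, 68% dropout, about 1,500 PY over 5 years, serious infection rates of 2.8 (reference) and 4.8 (alternative) per 100 PY, two-sided alpha 0.05, power about 97%. From Section 6.1.1: entry up to 24 months after first dose.

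**The plan's own figures.**
- Expected events are 1,500 × 0.028 = 42 and 1,500 × 0.048 = 72. An exact Poisson test (upper tail 0.025) rejects at 56 or more events, with power 97.8%. The stated 97% is reproduced.
- Constant dropout hazard λ = −ln(0.32)/5 = 0.228 per year. PY over 5 years = 500 × (1 − 0.32)/0.228 = 1,492, which matches the planned 1,500.

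**One pooled rate fits several patterns.** Forty-two events in 1,500 PY (2.8 per 100 PY, 95% CI 2.0 to 3.8) arise from a flat rate. They also arise from Year 1 at three times the later rate (5.3 v 1.8) and from Years 4-5 at three times the rate of Years 1-3 (5.4 v 1.8).

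**Late change.** Assumption: the same hazard continues to Year 10.
- PY to Year 10 = 500 × (1 − 0.32²)/0.228 = 1,969. Years 6-10 hold 1,969 − 1,492 = 477 PY, or 24.2%.
- Let the rate be 2.8 up to Year 5 and 5.6 after. Expected events = 1,492 × 0.028 + 477 × 0.056 = 41.8 + 26.7 = 68.5. Pooled rate = 68.5/1,969 = 3.48 per 100 PY, a rise of 24%.
- A flat 2.8 gives 55 events, 95% CI 2.10 to 3.64, and 3.48 lies inside it.
- Pooled exact test against 2.8: reject at 71 or more events, power about 40%.
- Years 6-10 v Years 1-5 (exact conditional test, two-sided 0.05): power about 72%.

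**Early change, registry person-time (10.3.2).** Roll-overs are left out. Registry PY per patient are 1,492/500 = 2.98 (5 years) and 1,969/500 = 3.94 (10 years). A threefold early rate raises the average by twice the early share.
- Entry uniform over 0-24 months after first dose (assumption): PY per patient within 6 months of first dose = ½ ∫₀^0.5 (1 − e^(−λ(0.5−u)))/λ du = 0.060, or 30 PY for 500 patients. The share is 2.0% (5 years) or 1.5% (10 years), so the average rises by 3% to 4%.
- All enter at first dose: 500 × (1 − e^(−0.5λ))/λ = 236 PY. The share is 15.8% or 12.0%, so the average rises by 24% to 32%.

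**Early change, total exposure (10.3.3), uniform entry.**
- Time before entry averages 1 year, so totals are 1,492 + 500 = 1,992 PY and 1,969 + 500 = 2,469 PY.
- First 6 months: before entry, 500 × (¼ × 0.25 + ¾ × 0.5) = 219 PY; after entry, 30 PY; together 249 PY. The share is 12.5% (5 years) or 10.1% (10 years), so a threefold early rate raises the average by 20% to 25%.
- Of those 249 PY, 219 (88%) precede entry. They rest on retrospective records that Section 6.6.2 asks for where available, and on patients who, under Section 6.1.1, were still on continuous therapy at entry.

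**AESI not collected after Year 5.** If 10-year PY are the denominator, the rate is multiplied by 1,492/1,969 = 0.76, so a true 2.8 would appear as 2.1. This does not touch SAEs, malignancy or CHF, which are collected throughout.

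**The case against.** The strongest reply is that no SAP is among the documents, that time bands are an ordinary table specification for a SAP, and that onset and dosing dates are collected, so nothing prevents them. This stands in part: the gap is in what the protocol plans, not in what the data allow. But Section 10.3 sets out the safety summaries down to denominators and windows and defers nothing on timing. The one explicit deferral to a SAP, in Section 10.4.1.4, comes in the effectiveness analyses.

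A reader might infer more than the documents support:

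- *That all four summaries are whole-period averages.* Section 10.3.4 compares rates before and after an interruption. That split is by interruption, in Humira patients who interrupted, so it does not address early or late risk.
- *That a change in risk could not be seen at all.* Successive cumulative reports under Section 10.5 could be differenced. That gives calendar time, not time since first dose, and is not planned.
- *That early treatment is almost absent.* This holds for registry person-time under uniform entry. The protocol gives no distribution of entry times, and Section 10.3.3 counts from the first recorded dose.
- *That the added five years were justified by late-onset events.* Section 10.6 cites low frequency, not latency. Pooling is a reasonable first estimate for rare events.

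The sparseness objection also stands. At 2.8 per 100 PY, 30 PY yield about 0.8 expected serious infections. With no malignancy in 477 PY, the upper 95% limit is still about 0.77 per 100 PY. Fine bands would say little there.

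**Conclusion.** The point holds in a limited form. The protocol plans no safety rate by time since first dose or by registry period, although its primary objective is long-term safety over 10 years. The pooled rates are valid averages and should stay.

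For serious infections the omission costs real information about late risk: a doubling after Year 5 shows as 3.5 instead of 2.8 per 100 PY and is detected about 40% of the time, against about 72% with a split at Year 5. This rests on carrying the plan's dropout for Humira exposure on to Year 10 as a constant hazard. The observational summary also counts off-drug and HCP follow-up time, so its late share may be larger.

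The early loss is less certain: the first 6 months are 1.5% to 2% of registry person-time under uniform entry, 12% to 16% if all enter at first dose, and about 10% to 12.5% of total exposure under uniform entry, where most of that time is retrospective and conditional on having stayed on drug. For malignancy and CHF a time split is descriptive only.

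**What to change.** Keep the pooled rates as the overall line. In Sections 10.3.2 and 10.3.3, or in the SAP with a reference from there, add:

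- Rates with 95% CI for serious infections and total SAEs by time since first recorded dose, for example up to 6 months, over 6 to 24 months, over 2 to 5 years, and over 5 years.
- A rule that a patient contributes person-time and events to a band only while under prospective observation.
- Malignancy and CHF in two bands only, up to 5 years and later.
- AESI no longer collected after Year 5 reported for Years 1-5 only.
- MTX shown descriptively in the same bands, in keeping with its role as reference group.

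Fix the bands before the data are examined. The dates needed are already collected (Sections 6.6.5 and 6.6.11); visits, treatment and sample size do not change. The cost is extra tables, with few events and wide intervals in some bands, above all the earliest band of Section 10.3.2 (about 30 PY under uniform entry). Label sparse bands as descriptive.

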## **6.1 Selection of Population**

Once a decision has been made between the physician and the patient to use Humira (monotherapy or combination therapy with MTX) or MTX (without Humira) as part of usual care for and in accordance with approved local prescribing information for polyarticular JIA, sites will be encouraged to offer enrollment to all eligible patients. After a decision to prescribe Humira, patients from previous Humira clinical trials (Study M10-444 and Study DE038) will be offered enrollment in the registry. Prior to collecting registry-related information, a parent or legal guardian must sign a parental consent and patient assent/authorization form, or appropriate forms per local requirements for release of information. Physicians should determine the appropriate therapy for each patient without regard to study participation. The participating physician will provide the patient a prescription for Humira (monotherapy or combination therapy with MTX) or MTX (without Humira) along with instructions for appropriate use in patients with moderately to severely polyarticular JIA.

Patients prescribed Humira rolling over from another AbbVie clinical study will continue in the Humira arm.

New patients may be enrolled in one of two arms, the Humira arm or the MTX arm, depending on the treatment decision made by the physician prior to enrollment.

Patients in the Humira arm may be treated with Humira alone or in combination with MTX.

Patients in the MTX arm may be treated with MTX alone or in combination with other DMARDs, but not with anti-TNFs or other biologic therapies.

Patients who are non-responders, intolerant to MTX treatment arm or are in need of combination treatment with Humira therapy are eligible to switch to the Humira treatment arm up until enrollment of the last patient into the registry (i.e., until enrollment in the Humira treatment arm is complete).

In these cases patients will be required to discontinue from the MTX arm and consent as a new patient in the Humira arm once any Adverse Events of Special Interest and SAEs have been resolved or the AbbVie Study Designated Physician should be contacted to assess the eligibility of a patient to enroll in the Humira treatment arm if an AE is ongoing and eligibility criteria are met.

The 10-year follow-up time for these patients begins when these patients start the Humira arm and not the date they started the registry within the MTX arm.

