### **6.1.2 Exclusion Criteria**

1. Patients should not be enrolled into the Humira or MTX arm if they cannot be prescribed and treated in accordance with the approved local Humira and/or with the local MTX product label.
2. Patients should not be enrolled into the Humira or MTX arm if they require ongoing treatment with Kineret® (anakinra), Orencia® (abatacept), Rituxan® (rituximab), Enbrel® (etanercept), Remicade® (infliximab) or any other approved biologic agents or investigational agents.

3. Patients should not be enrolled into the MTX arm if they have had prior treatment with any investigational agent or anti-rheumatic biologic therapy such as, but not limited to, Oencia® (abatacept), Enbrel® (etanercept), Remicade® (inflixumab), Rituxan® (rituximab), or Actemra® (tocilizumab).

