## **6.6 Registry Conduct**

Physicians will be provided with a registry kit that includes a protocol, parental informed consent and patient assent forms, and information material to enable access to electronic Case Report Forms (eCRF), including Serious Adverse Event (SAE) Report Forms, and specially designed eCRFs to collect assessment data and AEs of Special Interest (AESI). When applicable, information about the effectiveness of Humira therapy will be provided by the patients and their physician. Effectiveness of therapy provided by the patient will be collected with paper patient questionnaires and visual analogue scales called patient reported outcomes (PROs) for selfadministered assessments, if part of routine clinical care. Physicians will determine the appropriate therapy for each patient in accordance with the locally approved label. The decision to prescribe Humira (monotherapy or combination therapy with MTX) or MTX (without Humira) to the patients should be made separately from the decision to enroll them into the registry.

The physician will follow the patient during regular office visits at intervals as determined by routine clinical practice or as recommended by national guidelines.

At the enrollment (baseline) visit, the Investigator will complete the Enrollment eCRFs by obtaining and recording all of the available required information. AEs of Special Interest (Section 7.1.3) in addition to hospitalizations and surgeries meeting SAE criteria (Section 7.1.4) that occurred prior to the enrollment (baseline) visit will be collected on a specially designed questionnaire for entry into EDC.

At subsequent visits corresponding to the intervals in the registry activities (Table 1), the Investigator will complete the appropriate eCRF by obtaining and recording all available

[figure not shown]

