### **6.6.2 Medical History**

A complete non-polyarticular JIA related medical and surgical history as well as a history of tobacco and alcohol use will be obtained from each patient at the enrollment visit. A list of each patient's specific polyarticular JIA related medical and surgical history should be recorded in addition to the disease category, activity and the disease onset. For patients rolling over from a previous Humira clinical study, any ongoing AEs and SAEs as well as medical conditions requiring concomitant medication treatment will be captured as medical history items. The onset type of the disease will be recorded, if available, while a detailed medical history will not be required, unless information was omitted upon entry to the prior AbbVie Humira clinical study.

Patients will be asked to provide retrospective SAEs, Adverse Events of Special Interest, and exposure to MTX and/or Humira data, if available upon consent, from the first dose of MTX and/or commercial Humira to entry into this registry.

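### In the All Treatment-Emergent summary only the Humira arm has pre-registry harms reported in clinical trials; MTX pre-entry harms are all retrospective, so the two rates are not ascertained alike

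*Supplement*

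**What the plan says.** **Who is in which arm.** Section 6.1: "Patients prescribed Humira rolling over from another AbbVie clinical study will continue in the Humira arm". Section 6.1.2 closes the other route: "Patients should not be enrolled into the MTX arm if they have had prior treatment with any investigational agent or anti-rheumatic biologic therapy".

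**Prior exposure at entry.** Section 6.1.1 sets the window for Humira patients who did not come from a trial as "Newly initiated (within 24 months of registry entry) on Humira therapy", and for the MTX arm as "initiated treatment within 24 months of registry entry". Roll-overs may enter "within 24 months of registry entry or, if longer, continuously treated at the same site", so their earlier exposure has no upper limit. All three groups need a physician who can supply available source documentation of SAEs, AEs of special interest (AESI) and dosing since the start of therapy.

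**Where pre-registry events come from.** For roll-overs, Section 10.3 counts events from the first study-drug dose in the earlier trial (leaving out DE038 double-blind placebo time), together with "any events reported by retrospective data collection, and events reported during this registry". For everyone else the source is Section 6.6.2: "Patients will be asked to provide retrospective SAEs, Adverse Events of Special Interest, and exposure to MTX and/or Humira data, if available upon consent". Section 9.0 places this capture at the enrollment visit. Section 6.6 describes the enrollment questionnaire more narrowly, as AESI "in addition to hospitalizations and surgeries meeting SAE criteria (Section 7.1.4) that occurred prior to the enrollment (baseline) visit will be collected".

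**Denominator.** Section 10.2 counts total exposure from the first recorded dose, less Humira treatment interruptions and DE038 double-blind placebo time. Section 10.3.3 gives one rate per 100 patient-years of that exposure to Humira or MTX. Sections 10.3.1 and 10.3.2 start at the first registry day and the first registry dose. None of the three sections separates roll-overs.

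**The concern.** A rate is comparable between groups only if events are found with similar completeness over all the person-time in the denominator. In 10.3.3 they are not. Trial time comes with adverse events reported during a clinical trial. Pre-entry time outside a trial comes with whatever the family can recall and the chart can document at enrollment. That the trial events were recorded prospectively is an inference from their source; the protocol does not use the word.

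The better-documented time sits in one arm only. If retrospective capture is incomplete, the MTX reference rate is diluted more than the Humira rate, provided the roll-overs' pre-registry time is mainly trial time. Part of any excess on Humira would then be an artifact of recording. Long-term safety of Humira is the primary objective and MTX is its stated reference group (Section 5.0), so readers will set the two rates side by side.

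A separate, weaker question concerns 10.3.1 and 10.3.2. These pool roll-overs with uncapped earlier exposure and patients who started within 24 months, so the two arms may be at different average stages of treatment.

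**Working it through.** **The plan's own figure.** The plan gives no figure for this point. Its one design calculation (Section 10.6) supplies an input, so I checked it. Expected serious infections are 1500 × 0.028 = 42 under the reference rate and 1500 × 0.048 = 72 under the alternative. Power = Φ((72 − 42 − 1.96√42)/√72) = 97.9%, and 97.8% with exact Poisson limits, against about 97% stated. The power is unaffected by this point. The input taken from it is 1500 / 500 = 3 registry years per Humira patient.

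**Assumptions** (not in the documents):
- 3 registry years also apply to MTX patients, and in-registry events are fully captured in both arms.
- Share of the Humira arm that are roll-overs, f: 10-30%.
- Trial years per roll-over, t: 1-5, fully captured.
- Pre-entry years for everyone else, p: 1-2 (2 is the limit set by the 24-month rule).
- Share of pre-entry events captured retrospectively, c: 50-90%.
- Equal true event rates in the two arms, constant over time.

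**Captured share of true events:**
- MTX: M = (3 + p·c) / (3 + p)
- Humira: H = (3 + f·t + (1 − f)·p·c) / (3 + f·t + (1 − f)·p)
- Apparent rate ratio = H / M; the true ratio is 1.

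| f | t | p | c | H | M | H/M |
|---|---|---|---|---|---|---|
| 10% | 1 | 1 | 90% | 0.978 | 0.975 | 1.003 |
| 20% | 3 | 2 | 75% | 0.923 | 0.900 | 1.026 |
| 20% | 3 | 2 | 50% | 0.846 | 0.800 | 1.058 |
| 30% | 5 | 2 | 50% | 0.881 | 0.800 | 1.102 |
| any | any | any | 100% | 1.000 | 1.000 | 1.000 |

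Second row in full: H = (3 + 0.6 + 0.8 × 2 × 0.75) / (3 + 0.6 + 1.6) = 4.8 / 5.2 = 0.923; M = (3 + 1.5) / 5 = 0.900; ratio 1.026.

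**Sensitivity to the gap between trial and registry.** The table treats all pre-registry time of roll-overs as trial time. Time on commercial Humira between trial and registry is retrospective for them too. Adding a 2-year gap to the second row gives H = (3 + 0.6 + 0.2 × 2 × 0.75 + 1.2) / (3 + 0.6 + 0.4 + 1.6) = 5.1 / 5.6 = 0.911, and the ratio falls to 0.911 / 0.900 = 1.012. A gap that is long relative to the trial time could take it below 1. In that row this happens when gap/(6 + gap) exceeds 2/5, that is, beyond 4 years. The upward direction therefore also rests on the roll-overs' mix of trial and commercial time.

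**Registry-start summaries.** Pre-registry events and time are outside both 10.3.1 and 10.3.2, so the mechanism above does not operate there. The remaining difference is time already on drug. Its effect depends on how event rates change with time on treatment, which the documents do not give, so no ratio is computed.

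**The case against.** **Source documentation is an entry condition.** Section 6.1.1 ties pre-entry harms to records as well as recall, which argues against very low capture. This stands, and is why the range above starts at 50%. But only available documentation is asked for, and completeness is not guaranteed.

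**The contrast is not purely Humira against MTX.** Newly initiated Humira patients have the same retrospective capture and the same 24-month window as the MTX arm, and roll-overs have some retrospective time. This stands too. It makes the pooled Humira rate a mixture, which is the reason for separating its parts.

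**Table columns are normally left to an SAP, and none is shown.** A split there cannot be excluded. What remains is that the protocol itself defines the pooled event set and a single rate over total exposure.

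**MTX is a descriptive reference.** There is no between-arm test; the only sizing calculation compares the Humira rate with the DE038 rate. The point therefore concerns interpretation, not power or alpha.

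**Stronger readings a reader might infer:**
- *A larger ascertainment bias.* With 228 roll-overs, 3 trial years each, 1 pre-entry year for everyone else and 25% capture, H = (1500 + 684 + 272 × 0.25) / (1500 + 684 + 272) = 0.917, M = (900 + 75) / 1200 = 0.813, and the ratio is 1.13. But 228 is the total enrolled in DE038, M10-240 and M10-444 (Section 3.0), while the roll-over sources are DE038 and M10-444. Nothing supports every patient rolling over, or 25% capture.
- *Humira flattered in 10.3.1 and 10.3.2 because roll-overs have passed a high-risk early period.* This needs an early excess of events, which no section states. The MTX arm may also enter with up to 24 months of its early period behind it.

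**Conclusion.** The point holds for the All Treatment-Emergent summary (10.3 and 10.3.3). Pre-registry harms in the two arms are obtained differently, the trial-reported kind is confined to the Humira arm, and the pre-registry time on drug from both sources is in the denominator. Under the assumptions set out above the artifact is modest: an apparent Humira/MTX ratio of about 1.00 to 1.10 when the truth is 1.00, and none if retrospective capture is complete. Roll-over numbers, trial years and capture are not in the documents, so the size cannot be fixed, and retrospective time among roll-overs would reduce it.

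Sections 10.3.1 and 10.3.2 do not share the ascertainment problem. They do mix stages of exposure, with direction and size unknown.

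The difference between Section 6.6 (AESI plus hospitalizations and surgeries meeting SAE criteria) and Sections 6.6.2 and 9.0 (retrospective SAEs and AESI without that limit) is a minor wording conflict. It applies to both arms and leaves a narrow residue, because AESI already include events judged probably or possibly related to treatment or leading to its discontinuation (Section 7.1.3).

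**What to change.** - **Section 10.3.3:** report events and person-years separately for pre-registry and in-registry time. Show roll-overs and newly initiated Humira patients in separate columns beside MTX, and keep the pooled Humira column. Newly initiated Humira against MTX is then the like-for-like comparison for how pre-entry harms were collected.
- **Sections 10.3.1 and 10.3.2:** add the same roll-over split to the rates as a supportive display.
- **Sections 6.6, 6.6.2 and 9.0:** reconcile what the enrollment questionnaire asks about earlier SAEs. This cannot recover events already missed in enrolled patients, so the report should say which version was used.

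The split needs no new data: the prior-study patient number is already recorded on the eCRF (Section 6.6.1), and the event and dose dates are needed for the planned rates anyway. The cost is extra table columns and wider confidence intervals within them. If an SAP already specifies the split, a cross-reference in the protocol is enough.
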